## **Study Protocol and Statistical Analysis Plan**

**Study design:** single-blinded, 2-arm, randomized controlled clinical trial comparing an ultrasonic activation as the test protocol and a non-activated irrigation protocol as the control regarding their effectiveness in reducing bacteria and endotoxin from root canals after chemo-mechanical preparation. The study is not operator blinded because of the various devices used during the irrigation protocols, but the data analysis is blind.

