### **Participants:**

**Criteria for inclusion:** patients with necrotic pulps and apical periodontitis in single rooted teeth or in 1 root with a single canal from multi-rooted teeth.

**Criteria for exclusion:** patients who had received antibiotics during the previous 3 months or had any general disease; non-restored teeth; periodontal pockets depths greater than 4 mm; and radiographic evidence of previous endodontic treatment, open apex, crown/root fracture, root resorption or calcifications.

**Sample size:** sample size was estimated based on the means and standard deviations of the pilot study using BioEstat 5.3 software (Mamiraua, AM, Brazil). Calculation of statistical significance was estimated using the Wilcoxon test (power of 80% and significance level of 5%). A sample size of 20 patients per group was calculated based on the results of the pilot study. Considering the dropouts, a final sample size of 25 patients per group was decided.

**Randomization:** block randomization method generated by an electronic online randomizer (Research Randomizer, [www.randomizer.org](http://www.randomizer.org)).

**Interventions:** final irrigation protocols after root canal preparation: ultrasonic irrigation (UI) and needle irrigation (NI) groups. In the UI group, the irrigant was activated by a smooth wire with 0.2 mm diameter and .01 taper (Irrisonic - Helse, Ribeirão Preto, SP, Brazil), driven by an piezoelectric ultrasonic device set at 10% power following the manufacturer's recommendations. The studied protocol consisted of 2 cycles of refreshment/ activation of 2.5% NaOCl (30 s each), followed by 2 cycles of refreshment/ activation of 17% EDTA and 2 cycles of refreshment/ activation of 2.5% NaOCl. In the NI group, the volume of the irrigants, their sequence, the depth and time of irrigation were similar to the UI group but with no-ultrasonic activation.

**Primary outcome measures:** bacteria quantification by qPCR using universal primers for the conserved regions of the 16S rRNA gene of the Bacteria domain.

**Secondary outcome measures:** quantification of endotoxin by the quantitative kinetic turbidimetric LAL assay (Pyrogent 5000, Lonza Group Ltd, Walkersville, MD, USA) following the manufacturer's instructions.

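### Does leaving the operator unblinded expose the canal sample behind the primary outcome to bias that the plan should prevent?

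*Combined protocol and SAP*

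**What the plan says.** The Study design paragraph calls the trial single-blinded without naming the blinded party, and gives its masking rule in one sentence: "The study is not operator blinded because of the various devices used during the irrigation protocols, but the data analysis is blind". Data analysis is the only step described as blind.

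Under Interventions, the arms differ only in "final irrigation protocols after root canal preparation: ultrasonic irrigation (UI) and needle irrigation (NI) groups". The primary outcome is "bacteria quantification by qPCR using universal primers for the conserved regions of the 16S rRNA gene", and the secondary outcome is endotoxin by a kinetic LAL assay. Both are laboratory readings.

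No section describes canal sampling: not when samples are taken, how, by whom, or whether that person knows the arm. Nor does the document say whether samples are coded for the laboratory. That at least one sample follows final irrigation is an inference, though a safe one. The aim concerns "effectiveness in reducing bacteria and endotoxin from root canals after chemo-mechanical preparation", and the Statistical analysis plan has a related-samples Wilcoxon test within groups and a Mann-Whitney test between them.

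On allocation, Randomization says only "block randomization method generated by an electronic online randomizer".

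**The concern.** The reason for unblinding is narrower than the unblinding itself. A device in use cannot be hidden from the person using it, but that ends when final irrigation ends. The sample for the primary outcome comes afterwards. If the irrigating operator also takes it, that person knows the arm of every patient.

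If collection is manual, as is likely but not stated, its thoroughness could affect how much bacterial DNA is recovered. A tendency to sample one arm more or less thoroughly would enter the data before any masked step. The assay would faithfully measure a biased sample and the blind analyst would faithfully compare it. The difference would lie in the last sample only, so analysing reductions instead of final counts would not remove it. The endotoxin result and the chi-squared comparisons of positive samples would presumably share the problem.

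At stake is a false claim that one irrigation protocol is better, or a true difference hidden by bias in the other direction.

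**Working it through.** **1. What the text supports.** The plan has no figure on masking to reproduce, so the first check is to read the statements side by side.

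| Question | Answer in the document |
|---|---|
| Is the operator blind? | No; devices given as the reason (Study design) |
| Is the analysis blind? | Yes (Study design) |
| Where do the arms differ? | Final irrigation only (Interventions) |
| Who takes the canal sample? | Not stated |
| Does that person know the arm? | Not stated |
| Are samples coded for the laboratory? | Not stated |

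The first three answers do not settle the last three. The document neither prescribes unmasked sampling nor excludes it.

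**2. What a sampling bias would do, if there were one.** Inputs: 25 per arm (Sample size) and a 5% level (Statistical analysis plan). Assumptions: two-sided test, normal data on the log scale, no true effect, and every last sample in one arm shifted by b SD. With the large-sample efficiency of 0.955 for the Mann-Whitney test,

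m = b × √0.955 / √(2/25), and P(positive) = 1 − Φ(1.96 − m) + Φ(−1.96 − m).

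For b = 0.2: m = 0.2 × 0.977 / 0.283 = 0.69, so P = 1 − Φ(1.27) + Φ(−2.65) = 0.102 + 0.004 = 0.106.

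| Assumed shift b (SD) | Formula | Simulation, 60,000 trials |
|---|---|---|
| 0 | 5.0% | 4.6% |
| 0.1 | 6.4% | about 6% (separate run, 20,000 trials) |
| 0.2 | 10.6% | 9.8% |
| 0.3 | 17.9% | 16.9% |
| 0.5 | 40.8% | 38.2% |

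The simulation uses the continuity-corrected test, which is slightly conservative. With half the samples undetectable, the rates for 0.2, 0.3 and 0.5 SD are 9.4, 15.8 and 35.5%, so the normal model does not drive the result.

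**3. Reductions instead of final counts.** With correlation r between the two samples, the SD of a reduction is √(2(1 − r)) times that of a count, so the shift becomes b/√(2(1 − r)). For b = 0.3 this is 0.25, 0.30 and 0.39 at r = 0.3, 0.5 and 0.7. Simulated positive rates for b = 0.2 / 0.3 / 0.5:

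- r = 0.3: 8.3 / 13.3 / 29.0%
- r = 0.5: 9.8 / 16.4 / 38.4%
- r = 0.7: 13.4 / 24.8 / 57.4%

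So reductions do not protect against this route. They do protect against a difference made during preparation, before a post-preparation sample: both samples then shift and the rate stays at 4.6 to 4.7%.

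**4. No ratio to the design effect.** Setting these shifts against the difference the trial can detect would need to know which Wilcoxon test underlies the sample size. At 20 per group and 80% power, the two-group form detects about 0.94 SD of the counts (simulated). The paired form detects about 0.64 SD of within-patient differences, a different scale. The pilot values are not given, so no ratio is used.

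**5. What each possible remedy would do.**

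- *Second person takes the sample, unaware of the arm.* Addresses the risk. Needs another trained person at up to 2 × 25 = 50 treatments.
- *Reveal the arm only after preparation.* Does not protect a sample taken after irrigation, when the operator knows the arm anyway.
- *Code samples before qPCR and LAL.* Protects the laboratory step, not collection; both outcomes are instrument readings.
- *Name the sampler, the list holder and the time of reveal.* Adds description and changes no procedure.

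**The case for a change.** The strongest case for acting is that masking the irrigator and masking the sampler are separate questions. The plan answers the first and passes over the second. An objective assay and a blind analyst both come too late. With 25 per arm, a modest shift is enough to double the false-positive rate, and a second sampler costs no extra patients, visits or assays.

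Much of this stands. The text is as described, a bias at collection could not be undone later, and the rates above were confirmed on rerunning.

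What does not stand is the step from silence to a flaw. The harm needs four things in sequence: collection is manual, its thoroughness moves the count, thoroughness differs systematically by arm, and the shift is large enough to matter. The document gives none of them, and if a masked person samples, the point disappears. In so short a document, with no sampling section at all, saying nothing about the sampler is weak evidence of a decision to leave that person unmasked.

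Nor is the remedy free. It needs extra trained staff at every treatment, to meet a risk of unknown size. It may also come too late: Interventions is written in the past tense ("In the UI group, the irrigant was activated by a smooth wire"), although the Statistical analysis plan is in the future tense. If treatment is complete, only disclosure remains.

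The absence of detail on list custody and concealment is a separate reporting omission; nothing shows that concealment failed.

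**Conclusion.** The observation is accurate, but it does not call for a change to the plan. The document states no rule that gives a wrong result. It leaves out who collects the sample and what that person knows. The one measure that would mask collection trades extra staff at up to 50 treatments against a bias whose existence and size are both unknown. Accepting an unblinded operator, with instrument-read outcomes and blind analysis, is a fair trade-off here.

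The remaining gap is one the investigators can fill in the trial report: who was blinded, who took the samples and whether they knew the arm, whether the same sampling steps were used in both arms, whether samples were coded for the laboratory, and when the assignment was revealed. Unmasked sampling, if it occurred, belongs among the limitations.

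The size is conditional throughout. The rates of about 10, 17 and 38% for 0.2, 0.3 and 0.5 SD rest on assumed shifts applied to every patient in one arm, with manual sampling and no true effect. At 0.1 SD the rate is about 6%, close to nominal. A sampling procedure known to be carried out by an unmasked person, without common steps in both arms, would strengthen the concern; one carried out by a masked person would end it.

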### **Participants:**

**Criteria for inclusion:** patients with necrotic pulps and apical periodontitis in single rooted teeth or in 1 root with a single canal from multi-rooted teeth.

**Criteria for exclusion:** patients who had received antibiotics during the previous 3 months or had any general disease; non-restored teeth; periodontal pockets depths greater than 4 mm; and radiographic evidence of previous endodontic treatment, open apex, crown/root fracture, root resorption or calcifications.

**Sample size:** sample size was estimated based on the means and standard deviations of the pilot study using BioEstat 5.3 software (Mamiraua, AM, Brazil). Calculation of statistical significance was estimated using the Wilcoxon test (power of 80% and significance level of 5%). A sample size of 20 patients per group was calculated based on the results of the pilot study. Considering the dropouts, a final sample size of 25 patients per group was decided.

**Randomization:** block randomization method generated by an electronic online randomizer (Research Randomizer, [www.randomizer.org](http://www.randomizer.org)).

**Interventions:** final irrigation protocols after root canal preparation: ultrasonic irrigation (UI) and needle irrigation (NI) groups. In the UI group, the irrigant was activated by a smooth wire with 0.2 mm diameter and .01 taper (Irrisonic - Helse, Ribeirão Preto, SP, Brazil), driven by an piezoelectric ultrasonic device set at 10% power following the manufacturer's recommendations. The studied protocol consisted of 2 cycles of refreshment/ activation of 2.5% NaOCl (30 s each), followed by 2 cycles of refreshment/ activation of 17% EDTA and 2 cycles of refreshment/ activation of 2.5% NaOCl. In the NI group, the volume of the irrigants, their sequence, the depth and time of irrigation were similar to the UI group but with no-ultrasonic activation.

**Primary outcome measures:** bacteria quantification by qPCR using universal primers for the conserved regions of the 16S rRNA gene of the Bacteria domain.

**Secondary outcome measures:** quantification of endotoxin by the quantitative kinetic turbidimetric LAL assay (Pyrogent 5000, Lonza Group Ltd, Walkersville, MD, USA) following the manufacturer's instructions.

**Statistical analysis plan:** data will be summarized and statistically analyzed with SPSS Statistics Desktop software (IBM Corporation, Armonk, NY, USA) using Wilcoxon test for related samples for intra-group analyses; Mann-Whitney test for quantitative analysis of bacteria and endotoxins between groups; and chi-squared tests for qualitative analysis (incidence of positive

samples for bacterial DNA and endotoxin). All analyses will be performed with a significance level of 5%.

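### The between-group Mann-Whitney test ignores the earlier sample and does not say whether it compares level or reduction; one pre-specified rank ANCOVA would settle both

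*Combined protocol and SAP*

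**What the plan says.** The Statistical analysis plan section names three tests. Within arms it plans a "Wilcoxon test for related samples for intra-group analyses". Between arms it plans a "Mann-Whitney test for quantitative analysis of bacteria and endotoxins between groups". For detection as a yes/no result it plans chi-squared tests on the proportion of positive samples. No covariate appears anywhere.

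The Primary outcome measures section defines the endpoint only as "bacteria quantification by qPCR using universal primers for the conserved regions of the 16S rRNA gene of the Bacteria domain", with no sampling time, scale or change score. The Study design section frames the aim as "effectiveness in reducing bacteria and endotoxin from root canals after chemo-mechanical preparation", which leans towards a reduction. The Interventions section places the randomised step at the "final irrigation protocols after root canal preparation".

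On size, the Sample size section says "A sample size of 20 patients per group was calculated based on the results of the pilot study", raised to 25 per group for dropouts. The pilot means and SDs are not given.

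**The concern.** A related-samples test needs at least two measurements per canal, so an earlier sample is implied. Its timing is not stated. Because randomisation concerns the final irrigation, a sample between preparation and final irrigation is the natural reading, but that is an inference.

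Two analysts could follow the plan faithfully and run different primary tests. Mann-Whitney on the post-irrigation level discards the earlier sample. Mann-Whitney on the reduction uses it at a fixed slope of one, which is costly when the two samples correlate weakly or when post-irrigation values fall below detection. The plan expects some negative samples, since it tests how often samples are positive.

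At stake are power in a trial of 20 to 25 per arm, a choice between level and reduction left open until data are seen, and exposure to chance baseline imbalance in the one trial that is run.

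**Working it through.** **Inputs from the documents.** 20 per group before dropout and 25 after; power 80%; significance level 5% (sidedness not stated, two-sided assumed).

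**Assumptions.** Effect size, SD, correlation ρ between the earlier and final log10 values, and non-detect rate are not given and are varied below.

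**1. The plan's own figure.** The 20 per group cannot be reproduced without the pilot values, so it is inverted. For a two-group comparison, d = (1.960 + 0.842) × √(2/20) = 0.89 SD. With the Mann-Whitney efficiency of 0.955 under normality, d = 2.802 × √(2/19.1) = 0.91 SD. In simulation, d = 0.93 gives about 80% power for Mann-Whitney on the level, and that value is used. This reads the sizing test as a two-group test. If it was the paired Wilcoxon, 20 implies a within-group standardised change of about 0.63 to 0.64 and says nothing about between-group power.

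**2. Analytic effect of the choice.** Relative to an unadjusted test on the level, the variance factor f is 1 − ρ² for baseline adjustment and 2(1 − ρ) for the reduction (equal SDs). Power at 20 per arm is Φ(2.802/√f − 1.960).

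| ρ | f adjusted | power | n per arm for 80% | f reduction | power |
|---|---|---|---|---|---|
| 0 | 1.00 | 80% | 20 | 2.0 | 51% |
| 0.3 | 0.91 | 84% | 19 | 1.4 | 66% |
| 0.5 | 0.75 | 90% | 15 | 1.0 | 80% |
| 0.7 | 0.51 | 97.5% | 11 | 0.6 | 95% |

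**3. Simulation.** 20 per arm, d = 0.93, 20,000 runs per cell, bivariate normal log10 values with equal SDs. Non-detects are post-irrigation values floored at the stated quantile of the needle-irrigation arm. Power (%):

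| Control non-detects | Test | ρ = 0 | 0.3 | 0.5 | 0.7 |
|---|---|---|---|---|---|
| none | Mann-Whitney, level | 79.2 | 80.0 | 79.6 | 79.1 |
| | Mann-Whitney, reduction | 50.1 | 65.5 | 79.4 | 95.1 |
| | Quade rank ANCOVA | 78.5 | 82.4 | 87.9 | 96.0 |
| | Normal-theory ANCOVA | 80.4 | 84.5 | 90.4 | 97.7 |
| 30% | Mann-Whitney, level | 72.8 | 73.1 | 72.8 | 72.8 |
| | Mann-Whitney, reduction | 23.2 | 28.8 | 34.9 | 46.0 |
| | Quade rank ANCOVA | 72.2 | 75.3 | 80.4 | 89.8 |
| | Normal-theory ANCOVA | 68.4 | 71.2 | 77.0 | 86.2 |
| 50% | Mann-Whitney, level | 64.1 | 63.8 | 63.3 | 63.4 |
| | Mann-Whitney, reduction | 12.4 | 14.4 | 16.4 | 18.7 |
| | Quade rank ANCOVA | 63.4 | 65.7 | 69.9 | 77.9 |
| | Normal-theory ANCOVA | 55.4 | 58.2 | 61.8 | 69.4 |

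Quade minus Mann-Whitney on the level is about −1, 2, 7 to 8 and 15 to 17 points across the four correlations. With 25 per arm it is about −1, 2, 6 to 7 and 10 to 14. Flooring 30% of baseline values as well (20 per arm, 50% post-irrigation non-detects) leaves the pattern unchanged: 63.0, 63.4, 63.6, 63.9 against 62.4, 64.9, 70.0, 78.8. Overall type I error was 4.6 to 5.3% for every method.

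**4. Chance imbalance.** The baseline difference has standard error √(2/20) = 0.316 SD. A gap above 0.5 SD has probability 2 × [1 − Φ(0.5/0.316)] = 11.4%; with 25 per arm it is 7.7%. In those trials, with 20 per arm and no non-detects, the false-positive rate of Mann-Whitney on the level is 5.4, 7.2, 12.4 and 20.1%. For Quade it is 3.5 to 4.8% in all scenarios.

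**The case against.** **The planned test is valid.** Mann-Whitney is a standard, named test that holds its error rate under randomisation, so preferring rank ANCOVA is a matter of efficiency. This stands, and nothing here claims bias or inflated overall error. It does not answer the undefined variable, which is a gap even at zero correlation.

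**The gain depends on an unknown effect as well as an unknown correlation.** This also stands. With 20 per arm and no non-detects, Quade's gain at correlations 0.3, 0.5 and 0.7 is about 2, 7 and 19 points for d = 0.5, about 1, 3 and 5 for d = 1.2, and at most 0.5 for d = 1.5, where power is near its ceiling anyway.

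**The non-detect scenarios need careful reading.** The 30% and 50% are control-arm rates. With d = 0.93, about 66% and 82% of ultrasonic-arm values are then floored. The correlations are those before flooring: at 50%, 0.7 becomes about 0.6 (control) and 0.44 (ultrasonic) in the observed data. The very low power for the reduction assumes equal SDs and flooring of post-irrigation values only.

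**The imbalance figures cover only some trials.** In the other 89%, Mann-Whitney on the level runs slightly below nominal, at about 4.7, 4.6, 3.8 and 3.1%, which is why it averages 5%. The argument is about the realised trial, not the long run.

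**The covariate may be a weak predictor.** If the only earlier sample precedes preparation, the correlation may be low and the gain close to nothing. The loss is then still under about 1 point.

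**Choosing the level sets aside an aim framed as reduction.** It does not: with the earlier sample as covariate on the log scale, analysing level or change gives the same treatment estimate.

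**Conclusion.** The concern holds and should be acted on. The plan does not define what its primary between-group test compares, and it leaves out an earlier measurement that its own paired test implies. The planned test is valid; the cost is efficiency and an open primary analysis.

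The adjustment is worth nothing to about 2 points of power at correlations of 0.3 or less, and about 6 to 17 points at 0.5 to 0.7, if the effect is near 0.93 SD. Leaving level or reduction open matters more: with no non-detects the two differ by about 29 points at zero correlation (79.2 − 50.1) and by 16 points the other way at 0.7 (95.1 − 79.1). Quade is never more than about 1 point below the better of the two in the scenarios run.

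Confidence is medium, because effect size, SDs, correlation, non-detect rate and sampling times are all assumed.

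**What to change.** State when each canal is sampled, and define the analysed variable as the post-irrigation level. Then pre-specify one primary between-group analysis, for example:

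> *Post-irrigation bacterial load will be compared between UI and NI by Quade rank ANCOVA, adjusting for the last sample taken before final irrigation. Values below the detection limit are tied at the lowest rank. The test is two-sided at 5%.*

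Use the same form for endotoxin. Keep the unadjusted Mann-Whitney on the level as a sensitivity analysis. Quade's test gives no effect estimate, so add a ratio with 95% CI from a log10 ANCOVA as supportive only, with its handling of non-detects fixed in advance. It should not be primary, since with 50% non-detects it can fall below Mann-Whitney (55 to 62% against 63 to 64% at correlations up to 0.5).

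The cost is a few sentences in the SAP and one extra step in SPSS: rank both samples over all patients, regress the post-irrigation ranks on the earlier ranks, and compare the residuals by arm. No new data are needed if the earlier sample is taken, as the paired test implies.

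### Does testing positivity with chi-squared at 20 to 25 patients per arm break the 5% level enough to require an exact test?

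*Combined protocol and SAP*

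**What the plan says.** The combined document's Statistical analysis plan has three kinds of analysis: paired Wilcoxon tests within groups, Mann-Whitney tests between groups for the quantities of bacteria and endotoxin, and "chi-squared tests for qualitative analysis (incidence of positive" "samples for bacterial DNA and endotoxin"). The last does not say whether the test is uncorrected Pearson or continuity-corrected, and gives no rule for small expected counts. One level applies throughout: "All analyses will be performed with a significance level of 5"%.

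Under Sample size, "A sample size of 20 patients per group was calculated based on the results of the pilot study", and after an allowance for losses "a final sample size of 25 patients per group was decided". That calculation used a Wilcoxon test on pilot means and standard deviations, so positivity was not the sizing endpoint. The named primary outcome is the qPCR quantity and the named secondary outcome is the endotoxin quantity. The document gives no expected positivity rates.

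**The concern.** Chi-squared relies on a large-sample approximation, and the usual rule of thumb asks for expected counts of at least 5. With equal arms, the smallest expected count is half the total number of positives (or of negatives, if fewer). It falls below 5 when pooled positivity is under 10/50 = 20% with 25 per arm, or under 10/40 = 25% with 20 per arm, and likewise above 80% or 75%. Canals sampled before or after disinfection might lie in those ranges.

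If the approximation failed there, the stated 5% level would not hold. A claim that one irrigation protocol leaves fewer positive canals could then depend on the test chosen. The result 4/25 against 0/25, for example, is significant by uncorrected chi-squared and not by Fisher's exact test.

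**Working it through.** **Inputs.** From the document: 20 and 25 patients per arm, a 5% level, chi-squared with no variant named. Assumed: two independent binomials with a common positivity rate p, taken across the whole range because the document gives none.

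**The plan's own figure.** The 20 per group cannot be reproduced, because the pilot means and standard deviations are not given. The step to 25 is consistent with a 20% dropout rate, 20/(1 − 0.20) = 25, but that rate is also not stated. Both arm sizes are therefore carried through.

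**One table by hand: 4/25 against 0/25.** With N = 50, n = 25 per arm and m = 4 positives, the cross-product difference is |4×25 − 0×21| = 100.

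- Pearson: X² = N·100²/(n·n·m·(N − m)) = 500,000/(25×25×4×46) = 500,000/115,000 = 4.35, p = 0.037.
- Continuity-corrected: 50×(100 − 25)²/115,000 = 281,250/115,000 = 2.45, p = 0.118.
- Fisher: 2×C(25,4)/C(50,4) = 2×12,650/230,300 = 0.110.
- Boschloo, by maximising over p: 0.065. Barnard: 0.041.

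The verdict on this table does depend on the test, and the two unconditional exact tests also disagree with each other.

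**True size.** For each test, the size at p is the sum of Bin(a; n, p)·Bin(b; n, p) over all tables (a, b) with p-value below 0.05. For uncorrected Pearson:

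| Common positivity | 20 per arm | 25 per arm |
|---|---|---|
| 5% | 1.2% | 2.0% |
| 10% | 3.9% | 4.9% |
| 20% | 5.0% | 5.5% |
| 30% | 5.3% | 5.4% |
| 50% | 4.3% | 6.5% |

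Maximum over all p:

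| Test | 20 per arm | 25 per arm |
|---|---|---|
| Pearson, uncorrected | 5.34% (p about 0.31) | 6.49% (p = 0.50) |
| Continuity-corrected | 2.2% | 3.3% |
| Fisher | 2.5% | 3.3% |
| Boschloo | 4.6% | 4.6% |

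Pearson exceeds 5% for p of about 0.17 to 0.38 and the mirror range with 20 per arm, and for about 0.105 to 0.895 with 25.

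**Is sparseness the cause?** At p = 0.10 an expected count falls below 5 in 97.5% of trials with 25 per arm and 99.5% with 20, yet Pearson's size there is 4.9% and 3.9%. At p = 0.20 those shares are 44% and 73%, and the size is 5.5% and 5.0%. The 6.5% peak is at p = 0.50, where tables are well filled. Using Fisher only when an expected count is below 5 leaves the maximum at 5.2% (20 per arm) and 6.5% (25 per arm), so the conventional safeguard would hardly change it.

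**Tables that change verdict.** Counting each pair of arms once, the tables significant by Pearson but not by Fisher are:

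| | 20 per arm | 25 per arm |
|---|---|---|
| Total | 14 | 23 |
| with an expected count below 5 | 4 | 6 |
| significant by Boschloo | 10 | 12 |
| not significant by Boschloo | 4 | 11 |

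The table 5/25 against 0/25 is in the supported set: Fisher 0.0502, Boschloo 0.033, Barnard 0.021.

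**Cost of switching.** The same enumeration under assumed true rates of 10% v 40%, 20% v 50%, 20% v 60% and 30% v 70%, at both arm sizes, gives a power loss against Pearson of about 8 to 14 points with Fisher and about 1 to 7 points with Boschloo.

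**The case for a change.** The best case for a change is that, at the planned enrolment, uncorrected Pearson exceeds 5% over about 79% of the range of positivity rates. Fisher's conservatism does not explain all the disagreement either: 11 tables with 25 per arm and 4 with 20 are significant by Pearson but not by Boschloo, and none goes the other way. With the variant unstated, an analyst who sees 4/25 against 0/25 could report 0.037 or 0.118. One sentence naming a test would close that.

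These facts stand. They show that naming a test would be tidier, but not that chi-squared is a wrong choice. The excess over most of that range is about half a point and reaches 1.5 points only with no dropout and positivity near 50%; with 20 per arm it is 0.3 points at most. If the continuity-corrected version is meant, there is no excess, and no table is significant by it but not by Fisher. The freedom to choose is real, but the four counts of a 2×2 table let any reader recompute every version. Boschloo is the strongest alternative, but preferring it means trading a small excess in level for a loss of power, and statisticians reasonably differ on that.

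**Conclusion.** No change follows. The suspected mechanism, sparse tables pushing the test above 5%, is not what happens: uncorrected Pearson is below 5% at 5% to 10% positivity, and its largest excess is in well-filled tables. What remains is a worst-case true size of 5.3% with 20 per arm or 6.5% with 25, against a power cost of 1 to 14 points for the exact alternatives in the scenarios examined. That is a fair trade-off on a supportive analysis. The quantitative primary and secondary comparisons use Mann-Whitney tests and are untouched, as is the sample size. The unstated variant is missing detail that an analyst can fill sensibly by saying which version was used and showing the counts.

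This rests on equal arms of 20 or 25, independent patients and the uncorrected reading of the test. Unequal arms of 20 and 25 give a maximum of 5.2%, and equal arms of 21 to 24 give 5.2% to 6.0%, so the conclusion does not turn on the exact numbers completing. The positivity rates and the power scenarios are assumptions, since the document supplies neither.
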